## 3.3.5.3 Locoregional therapy

Any subject receiving locoregional therapy, including surgery, while on study that directly affects one or more of the target lesions selected at baseline and/or new lesions included in tumor burden will be identified. A subject with a subsequent response or SD/irSD will be considered to be non-evaluable at all disease assessments that occur on or after the date of locoregional therapy. Otherwise, the subject will be assessed ignoring the locoregional therapy.

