#### 3.3.5.1 RECIST 1.1 Derivations

#### **DERIVATION OF TARGET LESION RESPONSE**

Target lesion response will be programmatically derived on the data collection instrument once RECIST 1.1 criteria are applied to the site personnel recorded target lesion measurements.

Possible values include:

- CR Complete Response
- PR Partial Response
- SD Stable Disease
- PD Progressive Disease
- NE Non-evaluable
- NA Not Applicable (set value for all post-baseline disease assessments only if no target lesions are identified at baseline)

The derivation for target lesion response is as follows (please note the order of the algorithm below is important):

- 1. If "Any Target Lesions Present" equals "No" on the *Target Lesions Baseline* CRF, then all post-baseline "Target Lesion Response" equals "NA".
- 2. Else, if "Percent Change from Nadir Sum of Diameters" is greater than or equal to 20% and the absolute increase from the nadir (defined as the "Total" for each post-

- baseline disease assessment minus the "Nadir Sum of Diameters") is greater than or equal to 5 mm, then "Target Lesion Response" equals "PD".
- Else, if "Not Done" is selected, or "Measurement" is left blank, or "Lesion no longer Measureable" is selected and equal to "NE", or "Lesion Intervention" is selected for any Target Lesion identified at Baseline, then "Target Lesion Response" equals "NE".
- 4. Else, if "Total Non-Lymph Node" equals "0" and all Lymph Node Target Lesion "Measurements" are less than "10" individually, then "Target Lesion Response" equals "CR".
  - a. Note: This step requires examining "Measurements" separately for Target Lesions with "Lymph Node" equal to "Yes" and "No".
- 5. Else, if "Percent Change from Baseline Sum of Diameters" is less than or equal to 30%, then "Target Lesion Response" equals "PR".
- 6. Else, "Target Lesion Response" equals "SD".

If a subject has a missing tumor measurement at a disease assessment for 1 or more target lesions, the sum of diameters (longest for non-nodal lesions, short axis for nodal lesions) will be reported for the remaining target lesions. These data will be used to indicate radiologic disease progression if the sum of diameters for the observed lesions increases at least 20% from the nadir sum of diameters of all lesions and demonstrates at least a 5 mm absolute increase from the nadir sum of diameters of all lesions, in spite of the missing data (or if other criteria for PD are met).

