#### **DETERMINATION OF NON-TARGET LESION RESPONSE**

Non-target lesion response will be assigned by site personnel following a qualitative overall assessment of all non-target lesions.

- CR Complete Response
  - O Disappearance of all non-target lesions and normalization of tumor marker level. All lymph nodes must be non-pathological in size (<10mm short axis)
- Non-CR/Non-PD Non-Complete Response / Non-Progressive Disease
  - Persistence of one or more non-target lesion(s) and/or maintenance of tumor marker level above the normal limits
- PD Progressive Disease
  - o Unequivocal progression of existing non-target lesions.
- NE Non-evaluable
- NA Not Applicable (set value for all post-baseline disease assessments only if no non-target lesions are identified at baseline)

Though non-target lesion responses are a subjective decision made by the site personnel, certain responses may be limited depending on the non-target lesion statuses recorded. An algorithm is provided below highlighting appropriate possible non-target lesion responses based on recorded data. Reaching a red box (•) signifies having reached the only allowable non-target lesion responses based on non-target lesion statuses. Reaching a green box (•) signifies having reached the end of the algorithm and more than one possible non-target lesion response is possible from which the Investigator may choose.

- 1. a) If no non-target lesions are identified at baseline, all post-baseline non-target lesion responses should equal NA.
  - b) Else, if any non-target lesions are identified at baseline, responses may be limited to CR, Non-CR/Non-PD, PD, NE (ie, responses of NA are not permitted). Go to Rule 2.
- 2. a) If all non-target lesions have a status are "Absent", the responses may be limited to CR.
  - b) Else, if at least one non-target lesion status is NOT "Absent", the responses may be limited to Non-CR/Non-PD, PD, NE (ie, responses of CR, NA are not permitted). Go to Rule 3.
- 3. a) If all non-target lesions have a status of "Unequivocal Progression", responses may be limited to PD.
  - b) Else, if no non-target lesions have a status of "Unequivocal Progression", responses may be limited to Non-CR/Non-PD, NE (ie, responses of CR, PD, NA are not permitted).

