#### Go to Rule 5.

- 4. a) If all non-target lesions have a status of "Non-evaluable" and/or "Not Done" is selected, responses may be limited to NE.
  - b) Else, if no non-target lesions have a status of "Non-evaluable" and "Not Done" is not selected, responses may be limited to Non-CR/Non-PD (ie, responses of CR, PD, NE, NA are not permitted).
  - c) Else, if at least one (but not all) non-target lesion has a status of "Non-evaluable" and/or "Not Done" is selected, the responses may be limited to Non-CR/Non-PD, NE

(ie, responses of CR, PD, NA are not permitted). ■ (*Note: No response has been eliminated as an option here.*)

- 5. a) If all non-target lesions have a status of "Non-evaluable" and/or "Not Done" is selected, responses may be limited to NE.
  - b) Else, if no non-target lesions have a status of "Non-evaluable" and "Not Done" is not selected, responses may be limited to Non-CR/Non-PD, PD (ie, responses of CR, NE, NA are not permitted).
  - c) Else, if at least one (but not all) non-target lesion has a status of "Non-evaluable" and/or "Not Done" is selected, the responses may be limited to Non-CR/Non-PD, PD, NE (ie, responses of CR, NA are not permitted).

(*Note: No response has been eliminated as an option here.*)

If a subject has a missing tumor status at a disease assessment for 1 or more non-target lesions, radiologic disease progression will be determined if the remaining non-target lesions qualitatively demonstrate unequivocal progression (or if other criteria for PD are met).

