#### **DERIVATION OF NON-TUMOR BURDEN RESPONSE**

Non-tumor burden will be programmatically derived on the data collection instrument once irRECIST criteria are applied to the site personnel recorded non-target lesion and new lesions not included in tumor burden.

- Absent Response assigned if all non-target lesions and new lesions not included in the tumor burden statuses equal Absent
- Present / Indeterminate Response assigned if any of the non-target lesions or new lesions not included in the tumor burden statuses do not equal Absent

If a subject has a missing tumor status at a disease assessment for 1 or more non-target lesions and/or new lesions not included in tumor burden, radiologic disease progression will be determined if the remaining non-target lesions and new lesions not included in tumor burden qualitatively demonstrate unequivocal progression (or if other criteria for irPD are met).

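### The locoregional-therapy rule omits non-target lesions, so a removed or ablated non-target lesion recorded as Absent can turn PR into CR or, in a subject without target lesions, create a false responder

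*SAP*

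**What the plan says.** SAP Section 3.3.5.3 identifies a subject when on-study locoregional therapy, including surgery, "directly affects one or more of the target lesions selected at baseline and/or new lesions included in tumor burden will be identified". Such a subject's later response or SD/irSD becomes non-evaluable from the date of therapy. The section ends: "Otherwise, the subject will be assessed ignoring the locoregional therapy".

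Target lesions have a second safeguard. In the target lesion derivation (Section 3.3.5.1, step 3), the response is NE when Lesion Intervention "is selected for any Target Lesion identified at Baseline", unless the earlier PD step is met. Section 3.3.5.2, step 3, does the same for lesions in tumor burden.

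The non-target rules have no such step. Rule 2a reads "If all non-target lesions have a status are 'Absent', the responses may be limited to CR". Rule 2b reads "if at least one non-target lesion status is NOT 'Absent', the responses may be limited to Non-CR/Non-PD, PD, NE". For non-tumor burden under irRECIST, Absent is the "Response assigned if all non-target lesions and new lesions not included in the tumor burden statuses equal Absent". None of these asks why a lesion is absent.

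**The concern.** The SAP accepts that local treatment of a lesion contaminates response. It protects target and tumor-burden lesions twice and the remaining lesions not at all. A non-target lesion that has been excised or ablated may well be recorded as Absent, because nothing in the SAP forbids it. The response category then reflects the procedure rather than the study drug. At stake are the CR share of BOR and, for subjects with no target lesions, the primary ORR in the expansion phase.

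**Working it through.** The SAP gives no figure on this point, so there is none to reproduce. The check traces its rules; sample size, power and alpha are unaffected.

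**Inputs.** The RECIST 1.1 disease response table and the non-target rules (Section 3.3.5.1); the irRECIST table (Section 3.3.5.2); planned arm sizes of 40 and 20 (Section 2.4).

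**Step 1: when does non-target CR arise?** Only when all non-target lesions are Absent (Rules 2a and 2b). Other recordings lead elsewhere; for example, Rules 4a and 5a read "If all non-target lesions have a status of 'Non-evaluable' and/or 'Not Done' is selected, responses may be limited to NE". If only some lesions are non-evaluable, CR is still not allowed. A missing status gives overall NE unless PD is met (the paragraph after the response table).

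**Step 2: overall response by the table, with no new lesion.**

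| Target | Non-target Non-CR/Non-PD | Non-target NE | Non-target CR (all Absent) | Change in ORR from CR |
|---|---|---|---|---|
| CR | PR | PR | CR | none |
| PR | PR | PR | PR | none |
| SD | SD | SD | SD | none |
| PD | PD | PD | PD | none |
| NE | NE | NE | NE | none |
| NA | SD | NE | CR | non-responder becomes responder |

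Only two rows change. With target CR, PR becomes CR and the subject is a responder either way. With target NA, a non-responder becomes a responder. Section 3.4.1.1 requires confirmation at least 4 weeks later, but an excised lesion will normally still be absent then.

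**Step 3: irRECIST.** irCR with Present / Indeterminate gives irPR; irCR with Absent gives irCR. Objective response counts both (Section 3.4.2), so that rate does not move. irNA with Absent gives Absent, not irCR.

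**Step 4: size per subject.** One false responder adds 1/40 = 2.5 points to the combination ORR or 1/20 = 5.0 points to the nivolumab ORR. The number of such subjects is not documented. Assuming 0 to 2 in one arm, purely for illustration, the range is 0 to 2/40 = 5.0 points or 0 to 2/20 = 10.0 points.

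**Step 5: would coding the treated lesion Non-evaluable be enough?** The table gives PR for target CR or PR with non-target NE, and SD for target SD with non-target NE. The paragraph after it makes the whole assessment NE when a non-target status is missing and PD is not met. If a Non-evaluable status is read as missing, the two conflict and a genuine target PR could become NE. The matching irNE sentence after the irRECIST table raises the same problem.

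**The case against.** The SAP nowhere says that an excised lesion is recorded as Absent. Sites record the status, Non-evaluable is available to them, and CRF instructions or the protocol may settle the coding. This stands: the gap is a path the rules allow, not a documented outcome. Irradiation in particular need not make a lesion absent.

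ORR moves by this route only for subjects without target lesions. The table provides for them, but the SAP does not show whether eligibility admits them. This also stands.

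Section 3.4.1.1 limits BOR to assessments before subsequent anticancer treatment. If local therapy counts as such, later assessments drop out and no false CR enters BOR or ORR. The SAP does not say whether it counts. Section 3.3.3 mentions such treatment after discontinuation of study treatment, but only to describe a summary, not to define the term. Section 3.3.5.3 handles on-study local therapy separately. The safeguard is possible but not established.

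The word Otherwise in Section 3.3.5.3 might refer only to flagged subjects who later progress. On that reading non-target therapy is still not caught.

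A reader might infer that any missing non-target lesion is scored as complete response. The rules say the opposite: missing, Not Done and Non-evaluable statuses do not give CR.

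**Conclusion.** The gap is real and narrow. A non-target lesion removed or ablated on study is outside Section 3.3.5.3 and has no Lesion Intervention step. If all non-target lesions are then recorded Absent, non-target CR is the only permitted response. With target CR this inflates the CR share of BOR and leaves ORR unchanged. With target NA it adds a false responder, worth 2.5 or 5.0 points of ORR according to arm. Under irRECIST only irPR to irCR changes the response category.

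This rests on three assumptions: the site records Absent, no new lesion appears, and local therapy does not trigger the BOR cut-off. The total effect cannot be computed and may be zero.

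Two stronger readings are not supported. One is that the primary ORR is shown to be biased, or biased differently by arm: the SAP gives no frequency of local therapy, overall or by arm. The other is that PFS or disease control is shown to be distorted because local therapy may forestall a non-target progression. That is possible in principle, but it depends on a progression that is never observed, and no documented figure supports it.

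**What to change.** 1. Extend Section 3.3.5.3 to non-target lesions and to new lesions outside tumor burden. From the date of locoregional therapy, the treated lesion cannot count as Absent for response. Treat it as Non-evaluable, with irRECIST non-tumor burden Present / Indeterminate. PD from any lesion still counts.
2. State that the RECIST 1.1 response table governs this case: target CR + NE = PR, target PR + NE = PR, target SD + NE = SD, target NA + NE = NE. Reconcile the missing-status paragraph after that table, and the matching irNE sentence in Section 3.3.5.2, so that a treated lesion is not handled as a missing status that makes the whole assessment NE or irNE.
3. State in Section 3.4.1.1 whether locoregional therapy counts as subsequent anticancer treatment for the BOR cut-off.

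The cost is a few sentences and a programming flag from the procedure and radiotherapy records. There is a small downside: a subject whose treated non-target lesion would have vanished anyway can be at most PR, or NE if there are no target lesions.

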#### 3.4.1.6 Progression-free Survival

Progression-free survival (PFS) is defined as the time from randomization (dose expansion) / the first dose of IP (dose escalation) until the first documentation of disease progression or death due to any cause, whichever occurs first, regardless of whether the subject receives subsequent anticancer therapy prior to progression. Subjects who have not progressed at the time of analysis will be censored at the time of the latest date of assessment from their last adequate progression free disease assessment. Censoring rules are presented in Table 3.2. PFS is defined in months as follows:

PFS (months) = (Date of PD/death or censoring – Date of randomization (dose expansion) / the first dose of IP (dose escalation) first dose of IP+1) / (365.25/12)

The median PFS and its 95% CI will be estimated using the Kaplan-Meier method. An 80% CI for median time *may* also be included.

For the expansion phase, the difference in PFS between treatment groups will be tested for significance with a logrank test. The hazard ratio for the two treatment groups with two-sided 95% CI will be estimated by a Cox proportional hazard model controlling for the prespecified stratification factors as explanatory variables in the model. The proportion of subjects progression free and alive at 6 months and associated 95% CI will be estimated using the Kaplan-Meier method.

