#### **CENSORING OF PFS**

Table 3.2 Summary of Censoring Guidelines for Efficacy Endpoints

| Situation   | Date of PD/Death or Censoring   | PFS Outcome                          |
|---|---|--------------------------------------|
| Documented Progressive Disease (PD)   | Date of earliest sign of PD   | Event                                |
| Death prior to second scheduled post-baseline disease assessment or after an adequate post-baseline disease assessment  | Date of death   | Event                                |
| No PD or death at time of analysis or lost to follow-up   | Date of last adequate progression-
free disease assessment   | Censored                             |
| Death or PD immediately after ≥ 2 consecutive missed or non-evaluable disease assessments   | Date of randomization (dose expansion) / the first dose of IP (dose escalation) or last progression-free disease assessment prior to missed or non-evaluable assessments, whichever occurred last | Censored                             |
| Initiation of subsequent anticancer treatment   | Date of last adequate progression-
free disease assessment prior to
initiation of subsequent anticancer
treatment  | Censored for
Sensitivity Analyses |
| No tumor assessment at baseline and no evidence of PD at first post-baseline disease assessment, OR  No tumor assessment post-first dose, and no death prior to second scheduled post-baseline disease assessment | Date of randomization (dose expansion) / the first dose of IP (dose escalation)   | Censored                             |

PD = progressive disease; PFS = progression-free survival

Subjects having missing lesion data at baseline or no disease assessments post-first dose will have PFS censored at the date of randomization (dose expansion) / the first dose of IP (dose

escalation) unless the subject dies prior to the second scheduled post-baseline disease assessment in which case the death date will qualify as a PFS event.

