If a subject has two or more consecutive completely missed or non-evaluable assessments followed immediately by death or an assessment showing radiologic disease progression, then the subject will be censored for PFS. PFS will be censored at the date of randomization (dose expansion) / the first dose of IP (dose escalation) or the last progression-free disease assessment prior to the missed or non-evaluable assessments, whichever occurred last. If a subject has two or more consecutive missed or non-evaluable assessments followed by an assessment showing no radiologic disease progression, then the assumption will be that the subject did not progress during the missed or non-evaluable assessments. Two or more consecutive assessments is defined as  $\geq 17$  weeks (two disease assessments as per protocol plus a 1 week visit window to allow for a late assessment) after the last evaluable post-baseline disease assessment.

Subjects remaining on study without radiologic disease progression or death at the time of analysis will be censored for PFS at the date of their last adequate disease assessment. An adequate assessment is one that has recorded measurements for all target lesions and statuses for all non-target lesions defined at baseline (ie, the last non-missing or non-evaluable disease assessment). Additionally, a sensitivity analysis may be performed censoring PFS at the date of the last progression-free disease assessment prior to initiation of subsequent anticancer treatment.

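### After locoregional therapy, a subject who first shows stable disease or response has every later scan set to non-evaluable, including one showing progression, so PFS and duration of response lose events according to outcome

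*SAP*

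**What the plan says.** SAP Section 3.3.5.3 (Locoregional therapy) applies to on-study local treatment, surgery included, of a baseline target lesion or of a new lesion in tumor burden. The rule reads: "A subject with a subsequent response or SD/irSD will be considered to be non-evaluable at all disease assessments that occur on or after the date" when that therapy was given. For everyone else: "Otherwise, the subject will be assessed ignoring the locoregional therapy".

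Other parts of the SAP bear on the same scans:

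- **Section 3.3.5.1, target lesion response.** The algorithm is stated to be order-dependent. Growth from nadir gives PD at step 2. A lesion intervention gives NE at step 3, which is reached only if step 2 is not met.
- **Section 3.3.5.1, disease response.** A new lesion, or PD in non-target lesions, gives overall PD whatever the target response. The closing paragraph on missing lesion data gives NE only when PD is not met in another way.
- **Section 3.3.5.4.** PD is dated at the first objective evidence from target, non-target or new lesions.
- **Section 3.4.1.6.** PFS runs to first progression or death, "regardless of whether the subject receives subsequent anticancer therapy prior to progression". Censoring for such therapy is secondary: "a sensitivity analysis may be performed censoring PFS at the date of the last progression-free disease assessment prior to initiation of subsequent anticancer treatment".
- **Table 3.2 and the text below it.** The situation "Death or PD immediately after ≥ 2 consecutive missed or non-evaluable disease assessments" is censored at the last progression-free assessment before the gap. Two or more assessments is defined as at least 17 weeks after the last evaluable one.
- **Section 3.4.1.5.** Duration of response takes its event and censoring dates from Table 3.2.

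**The concern.** The locoregional rule works on the subject, not on the scan, and it is triggered by what happens after the therapy. If the first scan afterwards shows progression, the therapy is ignored and the progression counts. If that scan shows stable disease or response, every scan from the therapy date becomes non-evaluable. A new lesion seen eight weeks later then has no place in the analysis.

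Whether a progression is counted therefore depends on the course after the intervention, which is informative censoring. The SAP tests PFS with a logrank test and estimates a Cox hazard ratio, with up to 40 and 20 subjects. In the nivolumab arm one subject is 1/20 = 5% of the arm. The study is open-label, so the use of local treatment could differ between arms. Duration of response is exposed in the same way.

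**Working it through.** The SAP gives no figure that depends on this rule, so there is none to reproduce. The check applies the rules to hypothetical subjects.

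**Inputs**

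- Scan interval: the 17-week definition is two assessments plus one week, so (17 − 1)/2 = 8 weeks.
- Assumed course: last evaluable scan SD at week 8, locoregional therapy at week 10, scans at weeks 16, 24 and 32.
- Censoring: with gap = week of PD or death − week of last evaluable scan, the outcome is an event if the gap is below 17 weeks. Otherwise it is censored at the last evaluable scan.
- *As written*: any SD or response after week 10 makes all scans from week 10 NE.
- *PD first*: scans after week 10 that show PD stay PD (the order in Section 3.3.5.1). The others become NE and still count toward the gap.

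| Course after therapy | As written | PD first |
|---|---|---|
| PD wk 16 | event wk 16 | event wk 16 |
| SD wk 16, PD wk 24, alive | censored wk 8 | event wk 24 (gap 24 − 8 = 16) |
| SD wk 16, PD wk 24, death wk 30 | censored wk 8 (gap 30 − 8 = 22) | event wk 24 |
| SD wk 16, PD wk 24, death just before wk 25 | event at death (gap just under 17) | event wk 24 |
| SD wk 16, death wk 20 | event wk 20 (gap 12) | event wk 20 |
| SD wk 16 and 24, death wk 30 | censored wk 8 (gap 22) | censored wk 8 |
| SD wk 16 and 24, PD wk 32 | censored wk 8 | censored wk 8 (gap 24) |

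**What the table shows**

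1. Rows 1 and 2 differ only in one intervening SD scan. As written, the first subject has an event and the second does not.
2. Taking the scans on study days 168 and 56 (the +1 in the SAP formula included), row 2 moves from an event at 168/(365.25/12) = 5.5 months to censoring at 56/(365.25/12) = 1.8 months.
3. As written, a PD that follows post-therapy SD or response is never the event. A death is lost only when the gap reaches 17 weeks.
4. Rows 6 and 7 are censored under both readings. Restoring PD alone is not enough, because scans made NE by the therapy still feed the gap rule.

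**Duration of response.** Take PR at week 8, confirmed at week 16, therapy at week 18, PR at week 24 and PD at week 32. As written, weeks 24 and 32 are NE and the duration is censored at 16 − 8 = 8 weeks. With PD first, the gap is 32 − 16 = 16 weeks, so there is an event at 32 − 8 = 24 weeks.

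**The case against.** **A scan-by-scan reading may have been meant.** Only the SD and response scans would become NE, which agrees with the order in Section 3.3.5.1. But the sentence covers all assessments from the therapy date and has no PD exception. Even on this reading, rows 6 and 7 stay censored.

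**The rule can be programmed as a later override.** This stands. A reader might infer that the passages cannot all be executed, but a specific subject-level rule can be run after the general derivation. The override still discards progressions that Sections 3.3.5.1 and 3.3.5.4 recognise, and does so by outcome.

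**The PFS definition may not be contradicted.** This also stands in part. Section 3.4.1.6 speaks of subsequent anticancer therapy, and Section 3.3.3 uses the similar term for treatment after study treatment stops. The locoregional rule concerns therapy on study, and the SAP never equates the two. The conflict with the PFS definition is therefore conditional; the conflict with the response derivations is not.

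**Deaths.** A reader might infer that all later deaths are censored. Table 3.2 and the 17-week definition do not support that: a death within 17 weeks of the last evaluable scan remains an event.

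**The nadir.** Keeping PD by target-lesion growth could create false progression if a sum lowered by the therapy became the nadir. This is a fair point, and the fix has to cover it.

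**Conclusion.** The point holds. As written, Section 3.3.5.3 removes a progression seen after post-therapy SD or response, while counting one seen at the first post-therapy scan. It is inconsistent with Sections 3.3.5.1 and 3.3.5.4. It also fits poorly with the PFS definition if locoregional therapy counts as anticancer therapy.

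For an affected subject the change is large: an event at week 24 becomes censoring at week 8, given 8-weekly scans and the assumed course. The number affected cannot be derived. A reader might assume that 5% to 10% of the 60 expansion subjects have local treatment, giving 3 to 6 lost events. The SAP supports no such rate, and those counts would be a ceiling, because a subject must also show SD or response first and then progress, or die beyond the 17-week limit. Neither the size nor the direction of any shift in the hazard ratio can be stated.

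A reader might also infer that the primary comparison is at risk. The documents do not support that for the repair: post-therapy CR and PR scans are non-evaluable before and after it, so objective response rate, on which the Go/NoGo rules rest, does not change. The consequence lies in PFS and duration of response, and the rule should be corrected before those are analysed.

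**What to change.** Amend Section 3.3.5.3, with a cross-reference from Table 3.2, to state that:

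1. The rule applies to individual assessments. After locoregional therapy to a target lesion or a new lesion in tumor burden, an assessment that would otherwise be CR, PR or SD (irCR, irPR or irSD) is NE (irNE).
2. PD and irPD criteria still apply at every later assessment. For RECIST 1.1 these include a new lesion or unequivocal non-target progression. Target-lesion or tumor-burden growth is judged against the nadir sum of all lesions, as Sections 3.3.5.1 and 3.3.5.2 already do when measurements are missing. Specify that the nadir comes from evaluable assessments, so that a sum reduced by the therapy cannot become the nadir.
3. PD and death keep their own dates.
4. Scans performed without PD, and set to NE only because of locoregional therapy, do not count toward the censoring rule for two or more consecutive missed or non-evaluable assessments. The 17-week interval then runs from the latest such scan. Rows 6 and 7 of the table become events at weeks 30 and 32, with gaps from week 24 of 6 and 8 weeks.

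Censoring at locoregional therapy may be kept as a sensitivity analysis, beside the one already foreseen for subsequent anticancer treatment. The cost is a few lines of SAP text and a little extra derivation work. No new data are needed, because lesion intervention is already recorded and used in Section 3.3.5.1.
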